Annex 1: Classifications

Classification of postoperative complications (Clavien-Dindo classification)(19):

- **Grade I.** Any deviation from the normal postoperative course not requiring pharmacological, endoscopic, radiological or surgical treatment. The following are allowed: antiemetics, antipyretics, analgesics, diuretics, electrolytes and physiotherapy. Includes drainage of the surgical wound infection on the hospital ward.
- **Grade II.** Use of other medication not included in Grade I (blood transfusion or parenteral nutrition).
- **Grade III.** Complications requiring surgical, radiological or endoscopic intervention:
 - **Grade IIIA.** Interventions without general anaesthesia.
 - **Grade IIIB.** Interventions under general anaesthesia.
- **Grade IV.** Severe complications requiring admission to the Intensive Care Unit.
 - **Grade IVA.** Organ failure, including dialysis.
 - **Grade IVB.** Multi-organ failure.
- **Grade V.** Death of the patient.

LVB classification (Strasberg)(5):

- **Type A.** Injury from small hepatic ducts draining from the hepatic bed or cystic duct.
- **Type B.** Aberrant right hepatic duct obstruction.
- **Type C.** Transverse section, without ligation of the aberrant right hepatic duct.
- **Type D.** Lateral lesion of the main bile duct.
- **Type E.** Lesions of the main hepatic duct.
 - **E1.** Lesion more than 2 cm from the confluence of the hepatic ducts.
 - **E2.** Lesion less than 2 cm from the confluence of the hepatic ducts.
 - **E3.** Hilar lesion with preservation of the confluence of the hepatic ducts.
 - **E4.** Destruction of the biliary confluence.
 - **E5.** Aberrant right hepatic duct lesion.

Grade of severity of acute cholecystitis (Tokyo Guidelines 2018)(20):

- **Grade I (mild).** Acute cholecystitis in a healthy patient, without organ dysfunction, only mild inflammatory changes in the gallbladder.
- **Grade II (moderate).** Acute cholecystitis accompanied by the following conditions:
 - Leukocytosis >18,000 mm³.
 - Palpable mass in the right upper quadrant of the abdomen.
 - Duration of the picture of more than 72 hours.
 - Marked local inflammation (biliary peritonitis, perivesicular abscess, liver abscess, gangrenous cholecystitis, emphysematous cholecystitis).
- **Grade III (severe). Cholecystitis associated with dysfunction of the following organs or systems:**
 - Cardiovascular dysfunction (hypotension requiring treatment with dopamine >5 ug/kg/min or any dose of dobutamine).
 - Neurological dysfunction (decreased level of consciousness).
 - Respiratory dysfunction (PaO₂/FiO₂ <300).
 - Renal dysfunction (oliguria, creatinine >2 mg/dl).
 - Liver dysfunction (PT-INR >1.5).
 - Haematological dysfunction (platelets <100,000/mm³).

Annex 2: Documentation upon delivery of the Protocol:

1. Essential documents and other documents provided

- 1.1. Researcher's file revised and complete in all its sections
- 1.2. Place for the maintenance of the Researcher's Archive. Detail
- 1.3. The submission of the Researcher's File assumes that all documentation is complete. Highlight, if appropriate, specially submitted or annotated documents. Examples:
 - 1.3.1. Contract(s) and agreement of the centre's management
 - 1.3.2. Authorisation by the competent health authority, e.g. AEMPS.
 - 1.3.3. Favourable opinion of the ECIC

2. Essential documents and other collected documents (if applicable)

- 2.1. Signing of the visit log (with the Investigation Team and/or Pharmacy as appropriate)
- 2.2. Signed CVs of researchers, collaborators and pharmacy personnel
- 2.3. Laboratory ranges
- 2.4. Laboratory and equipment certificates. Accreditations
- 2.5. Signed Declaration of Conflict of Interest forms (if applicable) / "Financial Disclosure".
- 2.6. Signed receipt of delivery of Researcher's File and other trial material
- 2.7. Signed receipt of delivery of medication
- 2.8. Page for registering signatures, functions and delegation of tasks
- 2.9. Training record (if applicable) specific to the project - on GCP, visit attendance, procedures for completing CRD, etc.

Annex 3 (attached separately): Patient Information Sheet - Informed Consent.

Annex 4 (attached separately): AAG Notification Form. Annex 5

(attached separately): Pregnancy Notification Form.

DOTIG CLINICAL TRIAL (NCT05419947) STATISTICAL ANALYSIS

Study promoter	Castilla y Institute of Health Sciences Studies Foundation (IECSCYL)- Institute of Biomedical Research of Salamanca (IBSAL)	
EUDRA CT number	2022-000904-36	
Promoter's Protocol Code	IBS-DOTIG-ECM-2202	
Title	Randomised clinical trial to evaluate the dose and time of administration of indocyanine green in near-infrared fluorescein cholangiography during laparoscopic cholecystectomy.	
Date	16/12/2022	

1. Working hypothesis. There are differences in the visualisation rates of extrahepatic biliary structures as a function of drug dose and time of administration.

To test the hypothesis, we created four intervention groups combining two doses (fixed dose of 2.5 mg and weight-adjusted dose ratio of 0.05 mg/kg body weight) and two administration times (15-30 minutes preoperatively and >3 hours preoperatively). The primary endpoints are dichotomous and polytomous qualitative variables.

Before analysing the main and secondary objectives, the groups (G1, G2, G3, G4) and their baseline characteristics should be compared in order to demonstrate that they are homogeneous and the randomisation has been correct. To do this, the following variables collected in the CRDe should be compared:

- Sex (male/female)
- Age (years)
- BMI (kg/m2)
- ASA classification (ASA I/II/III/IV/IV/V)
- Previous abdominal surgeries (NO/SI). In the YES group, break down the variables biliary/liver/pancreas/intestinal/other).
- Previous liver disease (NO/SI). In the SI group, break down the variables: fatty liver disease, hepatitis, liver cirrhosis.
- Previous biliary examinations (NO/SI). In the SI group, break down the ERCP/CTPH variables.
- Previous biliary prostheses (NO/YES)
- Previous acute cholecystitis (NO/SI).
- Previous acute cholangitis (NO/SI).

- Previous gallbladder drainage (NO/SI). In the SI group, break down the variables percutaneous cholecystostomy/endoscopic cholecystostomy.
- Indication for surgery (biliary colic/acute cholecystitis/choledocholithiasis/acute cholangitis/acute lithiasic pancreatitis/bladder polyps/bladder adenomyomatosis).
- Type of surgery (elective/early/deferred surgery). Probably in this variable we do not have a very similar N, because most of them, at least in our centre, were elective.
- Grade of cholecystitis (1/2/3). In case of early indication/delayed urgency.
- Imaging system (Olympus/Karl-Storz/Stryker)
- Type of optics (30 degrees/ 0 degrees).
- 2. Main objective. To analyse whether there are differences between different doses (single dose and weight-adjusted dose) and different VI administration intervals in the visualisation rates of extrahepatic biliary structures.

Carry out a comparative analysis between the different groups (G1/G2/G3/G4) and the following qualitative variables:

- Identification of biliary structures prior to dissection of the hepatocystic triangle.

o Identification of cystic duct (yes/no).

o Identification of common bile duct (Y/N).

 ${\bf o}$ Identification of the junction of the cystic duct with the common bile duct (Y/N).

- **o** Identification of the junction of the cystic duct with the gall bladder (Y/N).
- **o** Identification of the common hepatic duct (Y/N).
- o Identification of anatomical variables (yes/no).

- Identification of biliary structures after dissection of the hepatocystic triangle.

o Identification of cystic duct (yes/no).
o Identification of common bile duct (Y/N).
o Identification of the junction of the cystic duct with the common bile duct (Y/N).

o Identification of the junction of the cystic duct with the gall bladder (yes/no).

o Identification of the common hepatic duct (Y/N).

o Identification of anatomical variables (yes/no.).

- Degree of identification of biliary structures prior to dissection of the hepatocystic triangle
 - 1=slightly 2=sufficient 3=quite a lot 4=good 5=excellent
- Degree of identification of biliary structures after dissection of the hepatocystic triangle:
 - 1=slightly 2=sufficient 3=quite a lot 4=good 5=excellent
- Extent to which fluorescence cholangiography was perceived to be useful for surgery
 - Not useful Moderately useful Very useful
- Extent to which the fluorescence of the liver background (contrast between liver and ducts) was perceived as disturbing.

0=absence of disturbance 1=slightly disturbed 2=disturbed visualisation, but cystic-choledochal junction was clearly visible before dissection 3= visualisation disturbed and the cystic-choledochal junction was visible only after dissection 4= very disturbed: it was impossible to visualise the biliary structures correctly.

3. Secondary objectives.

In these secondary objectives, we tried to analyse predictors of the quality of the fluorescence technique. To this end, we have found numerous factors in the literature that could influence cholangiography. We want to show whether there are differences between the factors listed below and the different working groups.

a) To analyse the influence of body mass index on FC outcomes during CL.

In this section, we could recode the qualitative variable BMI into the different BMI subgroups defined by the World Health Organisation or use normal weight/overweight as the cut-off point.

Clasificación	IMC (Kg/m ²
Normal	18.5 - 24.9
Sobrepeso	25 - 29.9
Obesidad grado I	30 - 34.9
Obesidad grado II	35 - 39.9
Obesidad grado III	Más de 40

We could also analyse it as a quantitative variable and see if there is a correlation between them.

b) To analyse the influence of the type of biliary pathology requiring surgery and previous liver disease on the results of FC during LC.

Analyse whether there are differences between "Previous liver disease (NO/SI). In the SI group, break down the variables: fatty liver disease, hepatitis, liver cirrhosis". And the main variables shown.

c) To analyse the influence of the type of surgery (elective/early/ delayed surgery) on the results of FC during LC.

To analyse whether there are differences between the variables "type of surgery" and "indication for surgery".

d) To analyse the influence of previous gallbladder or bile duct instrumentation on the results of FC during LC.

To analyse whether there are differences between the variables "previous biliary explorations", "previous biliary prostheses" and "previous gallbladder drainage". Both separately and united in a single variable.

e) To analyse the influence of different laparoscopic imaging systems on the results of FC during LC.

To analyse whether there are differences between the variable "image system" and the main target variables.

f) To analyse the rate of intraoperative complications related to CF during LC.

To analyse intraoperative complication rates in the series.

g) To analyse the rate of postoperative complications related to CF during LC.

To analyse the postoperative complication rate for the series overall and for each type of Clavien-Dindo classification (consecutive variable).

Also to analyse separately the rate of bile duct injury and the characteristics of bile duct injuries (consecutive variables).

Analyse in-hospital and 30-day mortality rates.

h) To analyse the impact of FC during LC on general surgeons and/or surgeons specialised in hepatobiliopancreatic pathology and their subjective assessment of the procedure.

To analyse this secondary objective, we should analyse globally the primary variable detailed above "Extent to which fluorescence cholangiography was perceived to be useful for surgery". We should also analyse it individually in each group.

- i) Analyse the rate and characteristics of late adverse reactions and AEs (separate Excel).
- j) To analyse the rate of anatomical variables (for this purpose we only analysed the variables (identification of biliary anatomical variables prior to dissection and the variable identification of biliary anatomical variables after dissection) globally.
- k) To analyse the influence of the technique on surgical time. To do so, we analysed the median complete surgical time (variable surgical time).

Note: in the study protocol we have put "Finally, all the statistical information obtained about the relevance of each variable in the study could be used to apply classification tools to the individuals in the study (decision trees, logistic regression, ROC curves)". I think this is a very interesting aspect but I need to talk about it and I need you to explain this section to me

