 - Indication for surgery [Symptomatic cholelithiasis (biliary colic, acute cholecystitis, choledocholithiasis, acute ascending cholangitis, acute lithiasic pancreatitis), gallbladder polyps, gallbladder adenomyomatosis].
- **Perioperative period:**
 - Date of entry (dd-mm-yyyy).
 - Time of entry (hour:minutes)
 - Date of surgery (dd-mm-yyyy).
 - Time of surgery (hour:minutes).

- Type of surgery (elective/early/ delayed emergency).
 - Grade of cholecystitis in case of early surgery / delayed emergency (18th Tokyo Classification).
 - Intervention group (group 1/group 2/group 3/group 4).
 - Characteristics of the procedure. IV dosage (fixed dose/weight-adjusted dose). IV administration interval (>3 hours preoperatively, 15-30 minutes preoperatively). Immediate adverse reactions (yes/no. Specify). Number of trocars (3/4). Imaging system used (Olympus/Karl-Storz/Stryker). Optics used (0º/30º). Gall bladder puncture/emptying (yes/no). Bile culture (yes/no). Result of bile culture if any (specify).
 - Conversion to laparotomy (yes/no), intraoperative complications (yes/no), specification of intraoperative complications (cystic artery injury, right hepatic artery injury, liver injury with/without bleeding, gallbladder opening (intrapertitoneal biliary contamination: yes/no, lithiasis outflow into peritoneal cavity: yes/no), hollow viscus perforation, trocar bleeding, other). Operating time (minutes).
- **Postoperative period:**
 - Hospital stay (days), postoperative complications (intra-abdominal haematoma, bilioma, abscess, paralytic ileus, surgical site infection-ISQ, trocar evisceration, trocar eventration, others), postoperative complications according to Clavien-Dindo classification, bile duct injury (Strasberg classification), time of diagnosis bile duct injury (intraoperative / postoperative), treatment of bile duct injury (immediate surgical, radiological, endoscopic or delayed surgical). Mortality during admission (yes/no), 30-day mortality (yes/no), causes of mortality (specify). Adverse drug reactions within 30 days (yes/no. Specify).

All preoperative data will be collected for patients withdrawn from the study, as well the type of complication developed and any adverse events during the first 30 days of the study (if any). Subjects will not be replaced in the study. The follow-up period will be identical for subjects who do not undergo the study intervention.

15. Monitoring

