20.12. Report to researchers

The sponsor will submit safety information that could impact the safety of the patients enrolled in the trial to the investigators as early as possible. In addition, the investigator will be informed throughout the study of any safety issues, including protocol modifications due to safety concerns.

21. Statistics

For the calculation of the sample size we estimated an average annual number of laparoscopic cholecystectomies of 300 cases. Assuming a minimum recruitment rate of 50% in the study, a duration of 12 months and possible losses of patients, we estimate a sample size of 200 patients.

Since the main objective is to analyse whether there are differences between the doses and administration times of the 4 treatment groups in which categorical variables will be measured, the effect of the chosen sample size ($n=200$) on the statistical contrasts in this type of variables is $w=0.25$ with a power.95 and a significance error of the null hypothesis $\alpha=0.05$.

The procedure used to account for missing, unused and erroneous data will be the "*Pairwise Delection*" method. The confidence intervals of the statistics will be 95% and the contrasts will be performed at a significance level of 5%. All analyses will be performed with the free software R (version 4.1.2+, R Core Team, Vienna, <https://www.R-project.org/>) and the RStudio interface (version 1.4.1103+).

The study will have no planned intermediate analyses as no partial analysis of results is envisaged. Once all data have been collected, verified and validated, a statistical analysis of the data will be performed according to the specifications described in the protocol. If this analysis leads to the conclusion that further analysis is necessary, this will be reported in the final analysis of results. All treated and evaluable subjects shall be analysed. Different statistical tools will be used depending on the nature of the variables collected in the study, accompanying the results with their corresponding graphs.

Lilliefors-Kolmogorov-Smirnov and Shapiro-Wilks tests shall be performed to study the normality of the distribution of quantitative variables, and to their distribution they shall be represented by the mean (standard deviation) or the median (median deviation) and may be accompanied by their corresponding confidence intervals. The relationship between such variables shall be measured with Pearson's or Spearman's correlation coefficients.

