The distributions of the categorical variables will be studied by means of frequencies and percentages. To represent and measure the dependence between them, contingency tables will be used with Pearson's Chi-square test, Fisher's exact test, McNemar's test

or Cochran's Q. A category comparison study could also be done using odds ratios between categories of clinical interest. To study the influence that some categorical variables might have on quantitative variables, ANOVA tests could be performed.

Finally, all the statistical information obtained on the relevance of each variable in the study could be used to apply classification tools to the individuals in the study (decision trees, logistic regression, ROC curves).

22. Direct Access to Source Data/Documents

The Promoter will enter into appropriate arrangements to appoint a monitor to oversee this study and to liaise regularly with the site, including arranging site visits. The investigator agrees to allow the monitor direct access to all relevant documents and to give his/her time and that of his/her staff to the monitor to discuss the results and any issues of concern.

23. Quality Control and Quality Assurance

In order to ensure the quality of the data, the promoter:

- Provide quality instruction and training to the research staff prior to the start of the study. Training topics include, but are not limited to: Good Clinical Practice (GCP) certificates, Adverse Event (AE) reporting, study details and procedures, study documentation, informed consent, and patient recruitment.

- Conduct regular monitoring in accordance with the International Conference on Harmonisation (ICH) for Good Clinical Practice (GCP). Data will be assessed for compliance with the protocol and for accuracy in relation to the source documents. Monitors will verify that the clinical trial is conducted, that data are generated, documented and reported in compliance with the protocol, good clinical practice and any applicable local regulatory requirements.

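### Comparing 16 variables across the four groups cannot demonstrate that the groups are homogeneous or that randomisation was correct

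*SAP*

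**What the plan says.** SAP section 1 puts a comparison step ahead of everything else: "Before analysing the main and secondary objectives, the groups (G1, G2, G3, G4) and their baseline characteristics should be compared". Its stated purpose is inferential: "in order to demonstrate that they are homogeneous and the randomisation has been correct". The SAP then says that "the following variables collected in the CRDe should be compared" and lists 16 items, from sex to type of optics. Four of them (previous abdominal surgery, liver disease, biliary examinations and gallbladder drainage) carry a further breakdown.

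The SAP names no test, threshold or consequence for this step. The protocol's section 21 (Statistics) supplies the general rules: "the contrasts will be performed at a significance level of 5" per cent. For categorical variables "contingency tables will be used with Pearson's Chi-square test, Fisher's exact test, McNemar's test" and related methods are listed, and for quantitative variables by category "ANOVA tests could be performed". No multiplicity adjustment is mentioned.

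One listed item is "Imaging system (Olympus/Karl-Storz/Stryker"), followed by type of optics. Protocol section 14 records both among the procedure characteristics of the perioperative period: "Imaging system used (Olympus/Karl-Storz/Stryker"). Under section 18, allocation is by unstratified 1:1:1:1 block randomisation, without blinding. Neither document pre-specifies covariates for the main comparison.

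**The concern.** The sentence asks the data for two things that a baseline comparison cannot give. A non-significant result does not show that groups are alike, least of all at about 50 per group. A significant result does not show that randomisation failed, because valid randomisation produces p<0.05 at the nominal rate by chance. Whether randomisation was correct is a question about how the allocation sequence was generated, concealed and followed. That is answered from the allocation records.

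Three things are at stake. A prognostic imbalance may be passed over because p>0.05. A chance finding may cast doubt on a sound trial. Or the baseline p-values may decide, after the data are seen, which covariates enter the analysis. The last is a live possibility: randomisation is unstratified in a multicentre trial, SAP section 3 says that many factors may influence cholangiography, and no adjustment set is fixed in advance. Protocol section 21 also leaves room for further analyses after the planned one.

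**Working it through.** **Inputs.** From the documents: 200 patients, two-sided 5% level (protocol section 21); four equal groups, so about 50 each (protocol section 18); 16 listed variables (counted in SAP section 1). The sizes of imbalance, prevalences and correlations below are assumptions, because the documents give none.

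**The plan's own figure.** There is none for this step. The only power figure is for the main contrasts: n=200, w=0.25, power 0.95. The noncentrality is 200 × 0.25² = 12.5, which gives power 0.94 at 1 df and 0.86 at 3 df. Nothing below depends on it, but w=0.25 is a useful yardstick.

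**Step 1: does non-significance show homogeneity?** For a yes/no variable in four groups of 50, the noncentrality is λ = 50 × Σ(pᵢ − p̄)² / [p̄(1 − p̄)], with 3 df and a critical value of 7.81.

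Example, 20%, 20%, 20% and 30%: p̄ = 0.225; Σ(pᵢ − p̄)² = 3 × 0.025² + 0.075² = 0.0075; λ = 50 × 0.0075 / 0.1744 = 2.15; w = √(2.15/200) = 0.10; power 20%.

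| Three groups vs the fourth | λ | Power |
|---|---|---|
| 20% vs 30% | 2.15 | 20% |
| 10% vs 20% | 3.43 | 31% |
| 40% vs 55% | 3.43 | 31% |
| 30% vs 45% | 3.77 | 34% |
| 5% vs 15% | 5.41 | 47% |

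For BMI shifted by d SD in one group, λ = 200 × d² × 3/16, tested by F with 3 and 196 df. At d = 0.3, λ = 3.375 and power is 30%. At 0.2, 0.4 and 0.5 SD, power is 15%, 51% and 72%.

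The same formula gives the test statistic if those percentages are what is observed. Counts of 10, 10, 10 and 15 out of 50 give χ² = 2.15, far below 7.81. A ten-point difference in one group would therefore be read as homogeneous.

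**Step 2: does significance show faulty randomisation?** If allocation was valid and all randomised patients are compared, the chance of at least one p<0.05 in k independent tests is 1 − 0.95ᵏ.

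- 16 variables: 1 − 0.95¹⁶ = 56%; expected number 16 × 0.05 = 0.8.
- 14 variables (without imaging system and optics): 1 − 0.95¹⁴ = 51%.
- 20 comparisons (each of the four breakdowns counted as one extra test): 64%. With all 12 breakdown categories tested separately, 28 comparisons: 76%.

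**Step 3: how far does that depend on independence and exact size?**

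- Permutation simulation with assumed prevalences, including several rare items, exact-type p-values and latent correlation of 0 to 0.3: 49–51% for the 16 variables, 55–58% with the four breakdown tables added.
- Equicorrelated 3-df statistics for 16 tests: 52%, 44% and 34% at correlations of 0.2, 0.4 and 0.6.

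**Step 4: imaging system and optics.** Protocol section 14 lists them under the perioperative period, but type of surgery and grade of cholecystitis stand under the same heading, so the heading does not settle timing. Type of surgery is tied to eligibility (protocol section 11.1: programmed, early or deferred), so it is known before allocation. Nothing comparable is said about when the imaging system or optics are chosen.

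**The case against.** The strongest reply is that the SAP asks only for a comparison. It names no test, and nowhere says that one p<0.05 among 16 means failed randomisation. That stands, and it rules out a tempting inference: that the plan, as written, will more likely than not declare randomisation incorrect. No such decision rule exists in either document. Testing is inferred from the protocol's general rules. The criticism of the sentence survives without that inference, though, because a purely descriptive table cannot demonstrate homogeneity or correct randomisation either.

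Second, 56% needs 16 independent tests of exact size. Several items are clinically linked (biliary examinations, prostheses and cholangitis; cholecystitis, drainage and indication), and Fisher's exact test is conservative in sparse tables. That also stands: the supportable statement is roughly an even chance, and less under strong correlation.

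Third, not every significant difference would be a chance finding. The protocol summary plans a per-protocol analysis and section 21 covers treated and evaluable subjects. Exclusions after allocation can create real differences even when randomisation was sound. In an open, blocked trial a marked imbalance can also be a fair reason to audit allocation. Both points stand. They are further reasons why a p-value in the analysed set cannot certify randomisation.

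Fourth, a reader might infer that imaging system and optics are post-allocation variables, or that this comparison was meant to replace covariate adjustment. The documents support neither. They are silent on when equipment is chosen, and no passage links the baseline comparison to the absence of adjustment.

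**Conclusion.** The stated inference is wrong as written and should be removed. Under the natural reading, the tests would miss most moderate imbalances: power is about 20–34% for shifts of 10–15 percentage points in one group from a base of 10% to 40%, or 0.3 SD of BMI. It is higher for larger shifts, such as 47% for 5% against 15%. They would also give at least one p<0.05 about half the time when nothing is wrong: 56% for 16 independent tests, 51% for 14, about 34–58% across the sensitivity runs.

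These figures rest on significance testing at 5%, about 50 analysed patients per group, and assumed imbalances, prevalences and correlations. Because no consequence is attached to a significant result, the harm is a risk of false reassurance, false alarm or data-driven covariate choice. It is not a certain misjudgement of the trial, and it does not by itself invalidate the main comparison. The change is worth making before analysis.

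**What to change.** 1. Delete the clause about demonstrating homogeneity and correct randomisation, and state that no baseline p-values will be produced.
2. Present the variables by arm descriptively, with standardised differences if wanted.
3. Verify randomisation from the allocation log and the electronic data-capture audit trail, and report the result.
4. Pre-specify adjustment of the main comparison for a few prognostic variables that are already collected and fixed before allocation, whatever the observed balance. Candidates are centre (identifiable from the patient code, protocol section 13), BMI and type of surgery.
5. Label imaging system and optics as procedural characteristics, and state when they are chosen relative to allocation.

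The cost is SAP wording for items 1, 2, 3 and 5. Item 4 adds modest modelling: regression alongside the contingency tables for the 12 yes/no and 4 graded endpoints in SAP section 2. With about 200 patients the covariate list must stay short, and the SAP should say what is done when an endpoint is close to 0% or 100% and the model may not fit. No new data are needed.
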